## **Abstract**

### **Background:**

Intraoperatively acquired pressure injure (IAPI) are a prevalent and important problem in the operating room (OR), and risk recognition by a quantifiable risk score is considered urgent in patients undergoing surgical procedure.

### **Objectives:**

Develop and validate a reliable and simple IAPI risk prediction model for surgical patients.

### **Design:**

A prospective, multicenter, cohort study.

### **Participants and setting:**

All patients who underwent surgery procedure from operating room of more than 5 tertiary hospitals in China.

### **Methods:**

We will use a pre-set observational assessment scale that consists of 24 indicators to construct the predictive model in this study. In addition to these pre-set indicators, the researchers will also collect other relevant indicators that they believe may contribute to the predictive model. Primary outcome was incidence of IAPI of any stage at 7 days from operating room admission. Secondary outcomes were in-hospital mortality (follow-up endpoint is 3 months after surgical procedure), surgical complication, and hospitalization costs. The prospective cohort study dataset is divided randomly into two

subsets: a training group (80% of the data) and an internal validation group (20% of the data). The training group is used for model development, while the internal validation group remains untouched until later stages. In model development, researchers can explore different variables and test various machine learning algorithms, such as logistic regression, artificial neural network (ANN), XGBoost, support vector machine (SVM), k-nearest neighbors (k-NN), naive Bayes, gradient boosting machines (GBM), AdaBoost, Gaussian mixture model (GMM), and support vector regression (SVR). They can train and optimize these models using the training dataset. After training the models on the training dataset, researchers can evaluate their performance using appropriate evaluation metrics (e.g., accuracy, precision, recall, F1-score, area under the receiver operating characteristics curve). Based on the evaluation results, we refine the model by tweaking hyperparameters, feature selection, or employing techniques like cross-validation or grid search. This iterative process aims to find the best-performing model configuration. Once the model is optimized using the training dataset, it is then evaluated on the internal validation dataset. This evaluation serves as an unbiased assessment of the model's performance on unseen data, providing an estimate of its ability to generalize. Based on the performance on the internal validation dataset, to choose the best-performing model as the final predictive model.

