factors such as changes in position, skin moisture, and nutritional status were also incorporated into the study. Each variable has three to four levels with operational definitions. Similar to the Norton scale, lower scores indicate a higher risk of PI occurrence with a "danger" threshold of  $\leq 16$  points for patients considered at high risk for developing PI. Although the Braden scale, Norton scale, and Waterlow scale all have good confidence, there is conflicting study evidence on the clinical validity of these risk assessment scales, and it is unclear which of these assessments is most important for clinical practice or whether combining them will result in better patient care. An early multicenter observational study showed that these risk assessment scales to a certain extent predicted the occurrence of PI, but the routine use of these scales would lead to inefficient use of preventive measures. The latest Cochrane systematic review shows that the value of using the Waterlow scale or other scoring scales for risk assessment in terms of PI incidence or severity is very small or no value compared with clinical judgment. The Cubbin & Jackson scale is a risk assessment scale developed for ICU patients, which is more suitable for the risk assessment of PI in ICU patients. The Munro scale is a risk assessment scale specifically designed for surgical PI risk, and recent studies have shown that the Munro scale has good IAPI risk assessment ability in surgical patients. However, the Munro scale includes 15 indicators of preoperative risks, intraoperative risks, and postoperative factors. Conducting the entire scoring system will require a lot of time and effort from staff. Implementing it in a busy surgical task may be an important challenge. And compared to nurses' clinical experience, this may be an inefficient work.

Here, the aims of this study to develop and validate a reliable and simple surgical patient IAPI risk prediction model by a prospective multicenter cohort data based on the combination of the indicators and practical experience of the most used assessment tools.

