#### **4.2 Data analysis**

This study is divided into two distinct sections. The aim of the first part is to create and validate a IAPI risk score for individuals from the whole cohort, predicting their individual IAPI values using a combination of potential predictive variables. The aim of the second part is to evaluate whether the IAPI score is helpful in predicting 90-day mortality in individuals from the whole cohort. We also evaluated the incidence and attributable mortality to IAPI, SSI, and surgical complications in patients admitted for

surgical procedures during the same study period.

All statistical analyses were performed with R (the latest version; R Foundation for Statistical Computing) and Python (the latest version; Python Software Foundation). All tests conducted in this study were 2-tailed, and  $P < 0.05$  was deemed statistically significant.

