#### ***4.2.1 Model development***

The entire cohort is randomly divided into two datasets: a training cohort (80%), which will potentially be utilized for training twelve machine learning models and optimizing their parameters, and an internal validation cohort (20%), which was employed to evaluate the developed models on unseen data and refine the hyperparameters.

The variable selection process in the development sample will be conducted using a recursive feature elimination (RFE) algorithm. RFE ranks the most relevant predictors in a dataset by training models with and without all potential predictor combinations. To identify the optimal number of variables, we will assess the incremental gain in predictive performance associated with each variable and stop at the inflection point. RFE is an iterative process that starts with all possible features in the dataset and progressively removes the least relevant features, building a model after each iteration. The goal is to find the optimal subset of features that maximizes the predictive power of the model. In each iteration, RFE evaluates the performance of the model with and without a specific feature and removes the feature if its removal results in a significant improvement in model performance. This process is repeated until the

desired number of features is reached or a stopping criterion is met. The inflexion point is the point at which the incremental gain in predictive performance begins to decrease significantly. Identifying the inflexion point helps to ensure that the final model does not overfit the data and can generalize well to new data. In conclusion, by using the RFE algorithm and identifying the inflexion point, the development sample will undergo a thorough variable selection process, ensuring that the final model is as predictive as possible while avoiding overfitting.

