After variable selection with RFE, we will be trained potential seven statistical models with centred and scaled selected predictors because of the different scales of the predictors and to ease the intercept of models to the IAPI, including a logistic regression, decision tree, random forest, artificial neural network (ANN), eXtreme Gradient Boosting algorithm (XGBoost), support vector machine (SVM), k-nearest neighbors (k-NN). Logistic regression is suitable for binary classification problems, while decision trees can handle both binary and multi-class problems. Random forests and XGBoost are based on decision trees and are known for their good performance in predicting both continuous and categorical variables. ANNs can be used for nonlinear problems, but they require more time for training. SVM and k-NN are also popular for classification problems, but they require different preprocessing techniques.

To evaluate the performance of each model, we will be using the cross-validation. With k-fold cross-validation, the data is randomly divided into k subsets, and each model is trained on k-1 subsets and tested on one subset. This process is repeated k times, with each of the k subsets being used once as the test set. The average

performance across all k tests is then used as the final performance measure. To assess the degree of potential over-fitting of each algorithm, we will be trained them using a 10-fold 10-repeat cross-validation procedure.

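### The final model is chosen on performance alone although the study promises a simple risk score, and the 4,115 sample size covers only a 24-parameter regression

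*Combined protocol and SAP*

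**What the plan says.** **The product.** The Abstract (Objectives) reads: "Develop and validate a reliable and simple IAPI risk prediction model for surgical patients". Section 2.2 repeats this aim. Section 4.2 describes a score: "The aim of the first part is to create and validate a IAPI risk score for individuals from the whole cohort". Its second part tests that score against 90-day mortality. Section 4.2.2 applies three cut-offs to the score and compares all models with five existing scales. Section 4.2.4.1 again gives simplicity as an aim. The Introduction explains why: "However, the Munro scale includes 15 indicators of preoperative risks, intraoperative risks, and postoperative factors", which it regards as too much work for a busy operating room.

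**The selection rule.** The Abstract (Methods) says: "Based on the performance on the internal validation dataset, to choose the best-performing model as the final predictive model". It lists accuracy, precision, recall, F1 and AUC as examples of metrics. None is named as the one that decides.

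**The candidates.** The Abstract names ten by way of example: "logistic regression, artificial neural network (ANN), XGBoost, support vector machine (SVM), k-nearest neighbors (k-NN), naive Bayes, gradient boosting machines (GBM), AdaBoost", then Gaussian mixture and support vector regression. Section 4.2.1 first describes a training cohort "which will potentially be utilized for training twelve machine learning models and optimizing their parameters", and after variable selection says: "we will be trained potential seven statistical models with centred and scaled selected predictors". Those seven are logistic regression, decision tree, random forest, neural network, XGBoost, support vector machine and k-nearest neighbours.

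**The points score.** Only Section 4.2.4.2 describes one. It derives points from a fitted logistic regression and calls that method attractive, under a heading about alternate analyses considered.

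**The sample size.** Section 4.1 uses one formula with 24 predictor parameters and a target shrinkage of 0.9. The result is 4,115 patients for development, 572 events and 23.83 events per parameter. The total is 5,144 after the 80/20 split.

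**The concern.** The rule for choosing the model is not tied to the product. A neural network or boosted ensemble that leads on the validation set becomes the final model, however small its lead. The plan gives no way to turn such a model into an additive points score for use at the bedside.

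Two outcomes are then possible. The study may end with a model that is not the simple score it promised. Or the team may go back to logistic regression to build points, and the reported AUC, calibration and cut-off results would belong to a different tool from the one issued.

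The sample-size statement adds to this. It reads as support for whichever model is developed, but its derivation covers only one kind of model with a fixed number of candidate parameters.

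**Working it through.** **1. Reproduce the plan's figure.** Inputs from Section 4.1: P = 24, S = 0.9, Cox-Snell R² = 0.051, outcome proportion 0.139.

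- n = P / [(S − 1) ln(1 − R²/S)] = 24 / [(−0.1) × ln(1 − 0.051/0.9)] = 4,114.1, so 4,115.
- Events: 4,115 × 0.139 = 572. Events per parameter: 572/24 = 23.83.
- Total: 4,115/0.8 = 5,143.75, so 5,144.

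All agree with the plan. The arithmetic is right for its inputs.

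**2. What the figure covers.** P is the number of candidate predictor parameters in a regression, and S is a uniform shrinkage factor for that regression. Section 4.1 mentions no other learner. The documents give no network architecture, number of trees or sample-size method for the other algorithms, so no required n can be computed for them.

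For scale only, assume one hidden layer of 10 units. Weights = 10 × inputs + 10 + 10 + 1.

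| Inputs (assumed) | Weights | Events per weight (572 events) |
|---|---|---|
| 5 | 71 | 8.1 |
| 14 | 161 | 3.6 |
| 24 | 261 | 2.2 |

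**3. Does it cover the regression route?** Section 4.2.1 starts feature elimination from every available feature. Table 1 numbers 50 items, then adds a 51st entry for other variables. At one parameter per item, which is a lenient count because most items have three or more categories:

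- n = 50 / [(−0.1) × ln(1 − 0.051/0.9)], which rounds up to 8,572 for development; 8,572/0.8 = 10,715 in total.
- Holding n at 4,115 with P = 50 and solving the same formula for S gives about 0.81 in place of 0.9. Events per parameter: 572/50 = 11.4.

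**4. How finely the validation set can separate models.** Size: 5,144 − 4,115 = 1,029 patients; 1,029 × 0.139 = 143 events. By the Hanley-McNeil formula, with an assumed AUC between 0.70 and 0.80, the 95% half-width for one model is about 0.050 to 0.045. Two models tested on the same patients are compared more precisely. The half-width of their difference is this value times √(2(1 − r)), where r is the correlation of the two AUC estimates; it is smaller than the single-model value once r exceeds 0.5. The documents give no r, so I put no number on the paired difference. With no margin specified, any lead decides, including one well inside that half-width.

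**5. The candidate lists side by side.** Ten in the Abstract; twelve, then seven, in Section 4.2.1. Adding decision tree and random forest to the Abstract's ten gives twelve, which may explain the larger count, but no section says so. The list of seven leaves out five of the Abstract's ten.

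**The case against.** **Simplicity is handled elsewhere.** Section 4.2.1 applies recursive feature elimination, stopping at an inflection point, before the algorithms are compared, and all seven are trained on the selected predictors. Section 4.2.4.1 harmonises categories. This stands: a reader who infers that the plan ignores simplicity would be wrong. The step limits the number of items, though with no stated maximum. It does not affect which kind of algorithm is chosen.

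**A machine-learning model can still give a risk score.** A reader might infer that a neural network or boosted trees could never deliver the promised score. The documents do not support that. Section 4.2.2 forms risk groups by cutting predicted risk, which any model that outputs a probability allows, and the objectives do not mention integer points. The gap is narrower: the only points score described comes from logistic regression.

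**The plan leans towards logistic regression and AUC.** Section 4.2.4.2 favours logistic regression, and Section 4.2.2 uses AUC for discrimination. Neither is made binding on the rule in the Abstract, and no margin is given.

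**Cross-validation guards against over-fitting.** Section 4.2.1 specifies 10-fold cross-validation repeated 10 times. That helps assess the complex learners, but it does not extend the 0.9 shrinkage target to them.

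**The 24 parameters may be the 50 items after merging.** Mobility, age and nutrition recur across the scales, and the Abstract speaks of 24 pre-set indicators. This is plausible, but no mapping is shown, and the Abstract also allows further indicators.

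**Conclusion.** The concern holds as a gap between the selection rule and the product, together with an overstated scope for the sample size. The rule can select an algorithm with no described route to points. Nothing says that the score issued is the one evaluated.

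The 4,115 patients, S = 0.9 and 23.83 events per parameter hold for a regression limited to 24 candidate parameters. They do not cover the other learners. Nor do they cover a regression whose selection starts from all 50 numbered items (about 8,572 for development, or S of about 0.81 at 4,115). Those last figures assume one parameter per item and the plan's R² of 0.051. The 1,029 patients and 143 events assume that the 5,144 are analysed at 13.9% incidence.

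Two further inferences are not supported:

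- A reader might enter a network's weight count as P in the plan's formula to get a required n. The formula is not a sample-size method for networks, so the weight counts above show scale only.
- A reader might set the 24 pre-set indicators against the 15 Munro items and conclude that the new tool will be longer. The 24 are candidates before selection, and the final number is not known.

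**What to change.** 1. **Selection rule (Abstract; Section 4.2.1).** Prespecify that the delivered risk score is the logistic-regression points score and report the other learners as comparators. Alternatively, prespecify one deciding metric and the margin by which a complex learner must exceed the points score to displace it.
2. **Evaluation (Section 4.2.2).** Compute AUC, calibration, cut-off results and the comparison with the five existing scales on the rounded points score that is issued.
3. **Sample size (Section 4.1).** State that 4,115 and S = 0.9 apply only to a regression limited to 24 candidate parameters, and show which Table 1 items make up the 24. If more candidates enter, recompute.
4. **Candidates.** Reconcile the ten, twelve and seven into one list.

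Items 1, 2 and 4 change wording or analysis only. They need no extra patients or data and should be settled before the validation data are examined. Item 3 is also wording only if candidates are held to 24 parameters. The cost is that a small AUC advantage of a complex learner, if there is one, may be reported but not adopted.

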## **Results:**

We describe the basic clinical characteristics of the patient underwent surgical procedure, and the incidence of primary outcomes (IAPI) and attributable mortality were reported. We will evaluate the performance of the model by assessing its accuracy,

precision, recall, and other relevant metrics. We will compare the predicted outcomes with the actual outcomes to determine the model's effectiveness in correctly predicting the outcome of interest. Additionally, we may also conduct statistical analyses to identify which indicators have the strongest predictive power and contribute the most to the model's performance. The results will be presented and interpreted in the study, providing valuable information about the model's reliability and potential applicability in future scenarios. The secondary outcome of this study is in-hospital mortality, surgical complications in patients during the same hospitalization will also be reported. Additionally, we evaluated the duration of hospital stay and associated costs incurred by patients within this hospitalization period.

**Conclusion:**

A robust predictive model that can accurately predict the desired outcome.

Using the PI risk assessment tool or scale is an integral part of the patient assessment process to determine if a patient has a risk of developing PI. The most commonly used risk assessment tools in clinical practice at present include the Norton scale, the Waterlow scale, the Braden scale, the Cubbin & Jackson scale, and the Munro scale. In the late 1950s and early 1960s, a team including doctors and nurses in London was committed to developing a risk assessment scale. Exton-Smith and Sherwin have shown that patients who change their body position more than 20 times per night during sleep have a lower risk of developing PI than those with less frequent changes in position. Clearly, changing positions is a factor. In addition to that in 1962, several other factors such as incontinence, activity, mental state, and physical condition were added to create the first risk assessment scale (Norton scale), with a lower score indicating a higher risk of PI. In the 1980s, the Norton scale played an important role in geriatric care units. A new tool, the Waterlow scale, was designed as a practical auxiliary tool for prevention and treatment while promoting understanding and identifying risk factors for patients experiencing PI, with a higher score indicating a higher risk of PI. The Braden scale is a scoring system developed at the same time as the Waterlow scale, which assesses the risk of pressure injury (PI). The Braden scale is designed based on literature reviews and reports of PI etiology. Braden and Bergstrom found that key factors were pressure intensity, duration, and tolerance. Other risk

factors such as changes in position, skin moisture, and nutritional status were also incorporated into the study. Each variable has three to four levels with operational definitions. Similar to the Norton scale, lower scores indicate a higher risk of PI occurrence with a "danger" threshold of  $\leq 16$  points for patients considered at high risk for developing PI. Although the Braden scale, Norton scale, and Waterlow scale all have good confidence, there is conflicting study evidence on the clinical validity of these risk assessment scales, and it is unclear which of these assessments is most important for clinical practice or whether combining them will result in better patient care. An early multicenter observational study showed that these risk assessment scales to a certain extent predicted the occurrence of PI, but the routine use of these scales would lead to inefficient use of preventive measures. The latest Cochrane systematic review shows that the value of using the Waterlow scale or other scoring scales for risk assessment in terms of PI incidence or severity is very small or no value compared with clinical judgment. The Cubbin & Jackson scale is a risk assessment scale developed for ICU patients, which is more suitable for the risk assessment of PI in ICU patients. The Munro scale is a risk assessment scale specifically designed for surgical PI risk, and recent studies have shown that the Munro scale has good IAPI risk assessment ability in surgical patients. However, the Munro scale includes 15 indicators of preoperative risks, intraoperative risks, and postoperative factors. Conducting the entire scoring system will require a lot of time and effort from staff. Implementing it in a busy surgical task may be an important challenge. And compared to nurses' clinical experience, this may be an inefficient work.

Here, the aims of this study to develop and validate a reliable and simple surgical patient IAPI risk prediction model by a prospective multicenter cohort data based on the combination of the indicators and practical experience of the most used assessment tools.

## **2. Methods**

### ***2.1 Study Design***

The proposed study design is a prospective, multicenter, cohort study, which aims to calculate the risk factors that influence the incidence of IAPI. This design allows researchers to observe the natural history of IAPI, and to identify potential risk factors and interventions that may affect the incidence of IAPI.

